19.3.2 Governance and Organizational Structure

- [name], her grant administrator [name], and the University of Pennsylvania will be responsible for the overall administration of the K23 grant funds for this trial. [name] will serve as the primary contact and be responsible for submission of all trial progress reports to (and communication with) the NHLBI at the NIH.

19.3.3 Dissemination of Findings and Scientific Responsibilities

- [name] will hold primary responsibility for data analysis and dissemination of research findings, including analysis of trial data (in consultation with collaborator [name]), presentation at scientific meetings, and manuscript drafting and submitting for peer review.

19.3.4 Funding Allocation

- Funding allocation will be carried out in accordance with the policies and procedures outlined by the University of Pennsylvania and the NIH. The Department of Anesthesiology and Critical Care is committed to the success of the applicant as an independent investigator and will provide all the resources required for the trial success (please see Institutional Commitment Letter for details).

19.4 Copy of the K23 Funded by the NHLBI of the NIH

- A copy of the K23 grant funded by NHLBI of the NIH is provided as an addendum to this protocol.

Clinical Study Number:	NCT06154265	Document Title:	10/24/2024	Page 35 of 36
		Default vs As-Needed Intraoperative Transesophageal Echocardiography (TEE) in Low-Risk Isolated Coronary Artery Bypass Graft (CABG) Surgery: A Randomized Controlled Trial		

19.5 Statistical Design and Power Analysis for the RCT

19.5.1 Statistical Analysis

- Descriptive statistics and frequency distributions will be calculated for: presurgical comorbidities, surgical characteristics, and perioperative factors for patients in each trial arm. Clinical data will be analyzed via intention-to-treat by Chi-squared and Wilcoxon rank-sum tests. Results from patient and cardiac surgeon satisfaction questionnaires will be collated and summarized using descriptive statistics. Means and proportions will be plotted to compare surgeon satisfaction with each trial arm.

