There is no randomized evidence to support the use of intraoperative TEE in any type of cardiac surgery. This evidence gap is particularly problematic in isolated CABG surgery for three reasons. First, in contrast to the comparative effectiveness studies that have associated intraoperative TEE with improved outcomes after cardiac valve,^{1, 2} proximal aortic,² observational research comparing clinical outcomes after isolated CABG surgeries with (vs without) intraoperative TEE have been equivocal.³⁻⁵ Second, observational research cannot confirm a causal link between intraoperative TEE and improved outcomes. This is especially problematic in isolated CABG surgery given how TEE is used during surgery. For instance, unlike the direct mechanism by which intraoperative TEE could improve outcomes in valve surgery (e.g. facilitating real-time surgical planning,^{6, 7} confirmation of pre-surgical valve pathology,^{8, 9} or immediate identification and resolution of a technical error in valve surgery and avoiding a return to the operating room),¹⁰ the mechanism by which intraoperative TEE could improve outcomes in isolated CABG surgery is indirect (e.g. hemodynamic monitoring by differentiating between cardiac failure¹¹⁻¹³ and hypovolemia).^{14, 15} Third, while life-threatening complications directly attributable to intraoperative TEE are rare (incidence of esophageal perforation from TEE is 0.01%),¹⁶ gastroesophageal injury from TEE after cardiac surgeries range 0.1% – 4%.¹⁷⁻²⁰ Thus, the true risk vs benefit of intraoperative TEE during isolated CABG surgery is unknown.

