10.2 Secondary Endpoint Analysis

Although this study is not powered to detect a difference in clinical outcomes between the default and as-needed intraoperative TEE groups, to plan for a future RCT that would be powered to detect a difference in clinical outcomes. We will collect clinical data on gastroesophageal dysfunction (symptoms or injury), incidence of end-organ dysfunction, and incidence of death as defined by the following:

1. Evidence of clinically-significant gastroesophageal dysfunction during hospitalization – either by patient-reported symptoms or by the presence of testing for swallowing difficulty, dysfunction, or upper endoscopy diagnostic procedures.
2. Evidence of end-organ dysfunction based on clinical notes (e.g. “transaminitis,” “acute kidney/renal injury”), and/or laboratory-based evidence of (e.g. liver function tests [LFTs], serum creatinine [Cr], lactate, etc.).
3. Incidence of in-hospital, post-surgical, cardiovascular re-intervention (e.g. return to the operating room for any reason, unplanned or emergency cardiac catheterization post-surgery, or placement on venoarterial extracorporeal membrane oxygenation [VAECMO]).
4. Incidence of all-cause in-hospital mortality

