10.3 Sample Size and Power Determination

- To account for screen failures (i.e., exclusions after enrollment), we are planning to obtain informed consent for up to 75 patients to ensure we achieve our enrollment goal of 22 patients randomized to each trial arm.

Clinical Study Number:	NCT06154265	Document Title:	10/24/2024	Page 18 of 36
		Default vs As-Needed Intraoperative Transesophageal Echocardiography (TEE) in Low-Risk Isolated Coronary Artery Bypass Graft (CABG) Surgery: A Randomized Controlled Trial		

11 Risk and Benefit Analysis

The standard-of-care intraoperative TEE device has passed quality assurance testing according to international regulatory guidelines. But specific to low-risk, isolated CABG surgery, the risk vs benefit profile for intraoperative TEE as an invasive hemodynamic monitoring device is currently unknown. Consequently, given that neither arm of the trial will be deprived of intraoperative TEE, the benefits of a greater understanding of who, when, and why intraoperative TEE should be used in isolated CABG surgery outweigh the risks in participating in a trial randomizing patients to two standard-of-care trial arms. The concrete risks associated with RCT participation and the steps put in place to mitigate these risks will be reviewed.

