19.5.2 Power Analysis

- Because the goal of this RCT is to assess study feasibility of a future trial, rather than efficacy comparisons, we did not conduct a formal power calculation. Rather, we established a sample size of 22 patients based on clinical expertise, annual PPMC isolated CABG surgical volume, and knowledge of operating room procedures. Given this low number of projected trial enrollment (n=22), this feasibility RCT will be underpowered to detect a difference in cardiac surgical outcomes. Nevertheless, we plan to review the electronic medical record for each study arm of the trial to compare any potential differences in clinical outcomes between the default and the as-needed intraoperative TEE trial arms.

Clinical Study Number:	NCT06154265	Document Title:	10/24/2024	Page 36 of 36
		Default vs As-Needed Intraoperative Transesophageal Echocardiography (TEE) in Low-Risk Isolated Coronary Artery Bypass Graft (CABG) Surgery: A Randomized Controlled Trial

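### Clinical outcomes are compared by chi-squared and Wilcoxon tests only; no confidence interval or between-arm estimate is planned, although the data are meant to plan a larger trial

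*Combined protocol and SAP*

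**What the plan says.** Section 19.5.1 provides descriptive statistics by arm for baseline, surgical and perioperative characteristics. For outcomes it says: "Clinical data will be analyzed via intention-to-treat by Chi-squared and Wilcoxon rank-sum tests". It does not say which test goes with which outcome, whether chi-squared is continuity-corrected, or what significance level applies.

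The purpose is stated in section 10.2: the clinical data are gathered "to plan for a future RCT that would be powered to detect a difference in clinical outcomes". Section 6.2 sets out to describe how often gastroesophageal problems occur, and the synopsis and section 10.2 list incidences of re-intervention and death.

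On size, section 10.3 refers to "our enrollment goal of 22 patients randomized to each trial arm", whereas section 19.5.2 gives 22 as the projected enrolment. Section 19.5.2 also states that "we did not conduct a formal power calculation" and that the trial will be underpowered for surgical outcomes. The only rate range given that bears on a clinical endpoint is in section 4: "gastroesophageal injury from TEE after cardiac surgeries range 0.1% – 4" percent. Section 11.1 repeats it as the risk of clinically significant injury.

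Section 19.5.1 adds: "Results from patient and cardiac surgeon satisfaction questionnaires will be collated and summarized using descriptive statistics". It also plans a plot comparing surgeon satisfaction between arms.

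**The concern.** Planning a powered trial needs the event rate in each arm, the difference between arms, and how far each could be from the truth. A P value from a comparison already declared underpowered supplies none of these. A non-significant result could be taken as reassurance when the data exclude very little. In the other direction, a sparse table could be called significant or not according to a software default.

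The satisfaction analysis raises a separate, smaller question: whether anything in the protocol produces the surgeon ratings it would plot. Ratings not taken around the time of surgery may not be recoverable later.

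**Working it through.** **Plan's own figure.** There is no power or precision calculation to reproduce. The accrual arithmetic in section 19.2.1.1 is 10 eligible per month × 12 × 20% = 24, close to 22 in total. Randomizing 44 would need 44/120 = 36.7%. Both 22 and 11 per arm are therefore carried below, assuming equal allocation.

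**Inputs.** Injury rate 0.1% to 4% (sections 4 and 11.1); 22 per arm (section 10.3) or 11 per arm (22 in total, section 19.5.2). A two-sided 5% level is my assumption, since none is stated.

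**Expected events per arm, n × p.**
- 22 per arm: 22 × 0.001 = 0.02; 22 × 0.04 = 0.88.
- 11 per arm: 0.01 to 0.44.

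**Chance of no event in either arm, (1 − p)^N.**
- N = 44: 0.999^44 = 95.7%; 0.96^44 = 16.6%.
- N = 22: 97.8% and 40.7%.

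In that case the expected event cells are zero and chi-squared is undefined. With equal arms the expected event count per arm is half the total, so 1 to 8 events in all give 0.5 to 4.0, below the customary 5.

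**One sparse table, 4/22 versus 0/22.**
- Uncorrected: 44 × (4×22 − 0×18)² / (4 × 40 × 22 × 22) = 4.40, P = 0.036.
- Yates: 44 × (88 − 22)² / 77,440 = 2.475, P = 0.116.
- Fisher: 2 × C(22,4)/C(44,4) = 2 × 7,315/135,751, P = 0.108.
- Newcombe 95% interval for the difference of 18.2 points: −0.2 to 38.5.

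**What zero events would leave open.** The Wilson upper limit for 0/n is z²/(n + z²), and for 0 versus 0 the Newcombe interval is ± that value.
- n = 22: 3.84/25.84 = 14.9 points.
- n = 11: 3.84/14.84 = 25.9 points.
- Exact (Clopper-Pearson) upper limit for one arm, 1 − 0.025^(1/n): 15.4% at n = 22; 28.5% at n = 11.

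**True size of the uncorrected test, by exact enumeration.**

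| Common rate | 22 per arm | 11 per arm |
|---|---|---|
| 4% | 0.9% | 0.1% |
| 10% | 4.3% | 1.2% |
| 20% | 5.1% | 3.4% |
| 40% | 4.7% | 4.9% |
| 50% | 4.9% | 5.3% |

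**If the symptom composite is common.** At 40% to 50% (an assumption; no rate is given), 22 per arm give 8.8 to 11 expected events per arm, and the chance of fewer than 10 in total is at most 0.5%. At 11 per arm that chance is 62% to 26%.

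**Satisfaction.** Sections 8.5.1 and 8.5.2 describe record review and two patient interviews, and the eight listed questions all concern symptoms. No surgeon form, item or time point appears there, and satisfaction is in no objective.

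**The case against.** Several stronger readings are tempting, and the documents do not support them.

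- A reader might infer that no rates will be reported. Section 6.2, the synopsis and section 10.2 all plan incidences; only their uncertainty and the between-arm estimate are missing.
- A reader might infer that every clinical outcome will be sparse. The 0.1% to 4% range concerns injury. The gastroesophageal endpoint also counts symptoms, and the interview asks about sore throat, nausea and reflux. No rate is given for that composite, organ dysfunction, re-intervention or death.
- A reader might infer inflated false positives. The enumeration shows otherwise: at 4% in both arms the uncorrected test rejects in 0.9% of trials, and does so without Fisher agreeing in about 0.7%. On that ground alone, choosing Fisher over Pearson would be largely a preference.
- A reader might include the Wilcoxon test in the criticism. Low event counts do not impair a rank test on measurements such as creatinine or lactate.
- A reader might infer that no satisfaction data will exist. Section 19.2.2 plans open-ended patient feedback on the protocol. Some pages, and the grant application cited in section 19.4, were not available, so an instrument may be described there.

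The plan also warns plainly that it is underpowered, which lowers the risk of over-reading a null result, and its primary endpoints concern process. These points narrow the concern. They do not supply the missing intervals, and a common composite needs them as much as a rare injury does.

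**Conclusion.** The concern holds in a limited form and should be fixed, but it touches secondary endpoints only. As written, the plan offers tests where its stated purpose calls for estimates with uncertainty. That conclusion needs no assumption about event rates.

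The criticism of chi-squared is narrower. It applies to outcomes as rare as the quoted injury range, where the test will often be incomputable or will depend on an unnamed variant. At 22 per arm it would be adequate for a composite running at 40% to 50%. The interval widths depend on whether 22 is per arm or in total, which the documents leave unreconciled.

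The surgeon-satisfaction comparison is a secondary point: it has no described data source in the text available.

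**What to change.** Replace the sentence in section 19.5.1 with a mapping of methods to outcomes:

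- **Binary outcomes:** n/N by randomized arm with exact 95% intervals, and the risk difference with a Newcombe or Miettinen-Nurminen 95% interval.
- **Continuous outcomes:** Hodges-Lehmann difference with 95% interval; the Wilcoxon test can stay beside it.
- **P values:** labelled exploratory, using an exact test where counts are sparse. Make the interval the primary summary, because the two can disagree: 4 versus 0 of 11 gives Fisher P = 0.090 but a Newcombe interval of 2.9 to 64.6 points.
- **Sample size:** reconcile sections 10.3, 19.2.1.1 and 19.5.2, then state the expected interval widths for the agreed number.
- **Satisfaction:** cite the existing instrument, or add a short surgeon rating and a patient item with their timing to section 8.5.2, or delete the analysis.

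The cost is a paragraph of text and a few lines of code, plus brief forms if satisfaction is kept. No extra patients are needed.

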8.4 Data Collection

8.5.1 Electronic Medical Record (EMR) Data Collection

- The PI ([name]) or other IRB-approved research personnel will collect post-surgical, clinical information from the electronic medical record, pre-surgically, and up to 5 days post-surgery. All data will be collected and securely stored on RedCap or on a single, password-protected, UPenn-regulated, laptop owned by the PI ([name]). No paper records will be kept.

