15.1 Source Data

Source data for this study will include:

- Protected Health Information (PHI) including: (1) name; (2) medical record number (MRN); (3) date of surgery

Electronic medical record (EMR) clinical data including: (1) medical and surgical history; (2) presurgical data and imaging (e.g. laboratory values, cardiac catheterization, transthoracic or transesophageal echocardiography, etc.); (3) intraoperative hemodynamic data (e.g. intraoperative blood pressure, pulmonary

Clinical Study Number:	NCT06154265	Document Title:	10/24/2024	Page 23 of 36
		Default vs As-Needed Intraoperative Transesophageal Echocardiography (TEE) in Low-Risk Isolated Coronary Artery Bypass Graft (CABG) Surgery: A Randomized Controlled Trial		

arterial pressure, mixed venous oxygen saturation, type and dose of intotropes, etc.); (4) postsurgical data and imaging (e.g. postsurgical care notes, laboratory values, imaging, etc.)

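### Continuous laboratory comparisons should be pre-specified as baseline-adjusted: Section 19.5.1 names only unadjusted tests and gives the presurgical values no role (minor, secondary analyses only)

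*Combined protocol and SAP*

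**What the plan says.** Section 19.5.1 gives the whole inferential plan for clinical outcomes in one sentence: "Clinical data will be analyzed via intention-to-treat by Chi-squared and Wilcoxon rank-sum tests". It names no covariate, regression, change score, effect estimate or confidence interval. Its only stated use of presurgical data is descriptive: "Descriptive statistics and frequency distributions will be calculated for: presurgical comorbidities, surgical characteristics, and perioperative factors for patients in each trial arm".

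The presurgical values are nevertheless collected. Section 8.5.1 covers "clinical information from the electronic medical record, pre-surgically, and up to 5 days post-surgery", and Section 15.1 lists "presurgical data and imaging (e.g. laboratory values, cardiac catheterization, transthoracic or transesophageal echocardiography, etc" as source data.

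The endpoint concerned is item 2 of Section 10.2, whose laboratory part is "laboratory-based evidence of (e.g. liver function tests [LFTs], serum creatinine [Cr], lactate, etc". No threshold, time point or scale is attached to it. The lead-in to the list speaks of "incidence of end-organ dysfunction, and incidence of death as defined by the following", which reads as a yes/no outcome.

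Two sample sizes appear. Section 10.3 has an "enrollment goal of 22 patients randomized to each trial arm", while Section 19.5.2 says "Given this low number of projected trial enrollment (n=22" for the trial as a whole.

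**The concern.** Of the four items in Section 10.2, re-intervention and death are yes/no, and gastroesophageal dysfunction is defined by symptoms being present or tests being done. Only the organ-function item contains continuous measurements, so it is the natural place in that list for the Wilcoxon test.

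If postoperative creatinine or liver tests are compared by a rank-sum test on the raw values, differences between patients that existed before surgery remain in the error term. A chance difference between arms before surgery also carries over into the arm comparison. Section 10.2 says the clinical data serve to plan a later, powered trial. For that use, an adjusted estimate with its confidence interval and residual SD tells more than a rank-test p-value. A trial this small has reason to use the precision available in data it already holds.

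**Working it through.** **The plan's own figure.** There is none to reproduce. Section 19.5.2 states that no formal power calculation was made, and no alpha, effect size or SD is given.

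**Inputs.** From the documents: n = 22 per arm (Section 10.3), or 22 in total (Section 19.5.2), which is 11 per arm if allocation is 1:1. The two must be reconciled, but that is a separate matter, so both are shown. Assumed: 1:1 allocation, two-sided alpha 0.05, values normal on the analysis scale (for example after logs), and a presurgical/postsurgical correlation ρ of 0.3 to 0.8. SD means the within-arm SD of the marker.

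**Variance.** Relative to an unadjusted difference in means, ANCOVA has variance factor (1 − ρ²) × (1 + 1/(2n − 4)). The second term is the price of estimating the slope: 1 + 1/40 = 1.025 at 22 per arm, and 1 + 1/18 = 1.056 at 11 per arm. For example, at ρ = 0.7 and 22 per arm, 0.51 × 1.025 = 0.523.

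**Detectable difference at 80% power.** Unadjusted: (1.960 + 0.842) × √(2/n), which is 0.845 SD at 22 per arm and 1.195 SD at 11 per arm. Adjusted: the same multiplied by the square root of the variance factor.

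| ρ | Variance factor, 22/arm | Detectable (SD), 22/arm | Variance factor, 11/arm | Detectable (SD), 11/arm |
|---|---|---|---|---|
| unadjusted | 1 | 0.845 | 1 | 1.195 |
| 0.3 | 0.93 | 0.816 | 0.96 | 1.171 |
| 0.5 | 0.77 | 0.741 | 0.79 | 1.063 |
| 0.7 | 0.52 | 0.611 | 0.54 | 0.876 |
| 0.8 | 0.37 | 0.513 | 0.38 | 0.736 |

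**Break-even.** The factor equals 1 when ρ² = 1/(2n − 3). That is ρ = √(1/41) = 0.16 at 22 per arm and √(1/19) = 0.23 at 11 per arm. Below this, adjustment costs a little: at ρ = 0 the factors are 1.025 and 1.056.

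**Simulated power against the Wilcoxon test itself** (10,000 runs per setting, true shift 0.5 SD):

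| ρ | Wilcoxon, raw | Wilcoxon, change | Rank ANCOVA | ANCOVA |
|---|---|---|---|---|
| 22/arm, 0.3 | 0.35 | 0.26 | 0.37 | 0.39 |
| 22/arm, 0.5 | 0.35 | 0.35 | 0.43 | 0.46 |
| 22/arm, 0.7 | 0.35 | 0.53 | 0.56 | 0.61 |
| 22/arm, 0.8 | 0.36 | 0.70 | 0.70 | 0.76 |
| 11/arm, 0.3 | 0.19 | 0.15 | 0.20 | 0.21 |
| 11/arm, 0.5 | 0.18 | 0.18 | 0.22 | 0.24 |
| 11/arm, 0.7 | 0.19 | 0.28 | 0.30 | 0.33 |
| 11/arm, 0.8 | 0.19 | 0.40 | 0.38 | 0.45 |

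**Chance imbalance.** The between-arm difference in baseline means has SD √(2/n): 0.30 at 22 per arm and 0.43 at 11 per arm. The probability that it exceeds 0.5 SD in either direction is 2 × [1 − Φ(0.5/0.30)] = 9.7% and 2 × [1 − Φ(0.5/0.43)] = 24.1%, using unrounded SDs. An imbalance of 0.5 SD moves the expected unadjusted difference by ρ × 0.5, which is 0.35 SD at ρ = 0.7.

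**Type I error.** Over all simulated null trials with ρ from 0.3 to 0.8, raw Wilcoxon rejects in 4.6% to 5.1% and ANCOVA in about 5%. Among only those null trials with imbalance above 0.5 SD, raw Wilcoxon rejects in 14% (ρ = 0.5) or 24% (ρ = 0.7) at 22 per arm, and in 9% or 14% at 11 per arm. ANCOVA stays near 5%.

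**The case against.** The strongest objection is that the plan may never make this comparison. Section 10.2 calls organ dysfunction an incidence, based on clinical notes and/or laboratory evidence, and nowhere says that creatinine, liver tests or lactate will be compared as continuous values. A reader might infer that the organ-function endpoint is to be tested by Wilcoxon on raw postoperative values. The documents do not support that. This limits the point to continuous laboratory comparisons, but does not remove it: Section 19.5.1 names a rank test, Section 19.5.2 plans to compare clinical outcomes between arms, and the missing threshold, time point and scale leave the choice open until after the data are seen.

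A reader might also infer that the plan discards baseline information. In fact it is silent: Section 19.5.1 does not say whether the rank test is applied to raw values or to change. Change scores would recover much of the gain when ρ is high, but do worse than raw values at ρ = 0.3.

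The correlation could be low. Section 6.3.2 excludes chronic kidney disease of stage 3 or worse and dialysis, which narrows the spread of presurgical creatinine. At ρ = 0.3 the variance falls only 4% to 7%. That stands.

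Three further objections stand. The residual SD could be computed later from the retained patient data whichever test is named. Section 15.1 does not show that every patient has every marker before surgery. The comparison is secondary and openly underpowered.

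**Conclusion.** The point holds in limited form. For any laboratory marker compared as a continuous value and measured before surgery, a pre-specified baseline-adjusted analysis is better than an unadjusted rank test. The gain depends on a correlation the documents do not give. Over the assumed range 0.3 to 0.8, variance falls by 7% to 63% at 22 per arm and by 4% to 62% at 11 per arm, under normality on the analysis scale and 1:1 allocation.

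A reader might infer from the imbalance figures that the planned test has an inflated false-positive rate. It does not: overall type I error is about 5%. Imbalance costs precision and makes a particular unbalanced sample hard to read.

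If organ dysfunction is analyzed only as yes/no, these figures do not apply. The primary endpoints in Section 10.1, recruitment and TEE use in the as-needed arm, are unaffected. This is a minor improvement to a secondary comparison.

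**What to change.** In Section 19.5.1:

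- State which laboratory measures are compared, at what time point within the 5-day window, and whether each is analyzed as continuous or yes/no.
- For each continuous measure with a presurgical value, make the main intention-to-treat comparison a model of the postoperative value on randomized arm and presurgical value. Use log-scale ANCOVA, or rank ANCOVA if the log scale is judged unsuitable.
- Report the adjusted estimate (on the log scale, a ratio of geometric means) with its 95% CI, and the residual SD.
- Keep the Wilcoxon test as a sensitivity analysis, and as the method for markers with no presurgical value.
- Say in advance how patients lacking a presurgical value are handled when others have one, so that none is dropped from the intention-to-treat set.

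The cost is a few sentences of analysis-plan wording, with no added visits or tests for markers already measured before surgery. The downside is a modelling assumption in a small sample, against which the retained Wilcoxon result is a check, and a slight loss of precision if the correlation is below about 0.16 (22 per arm) or 0.23 (11 per arm).
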